**Table 1. Histologic classification of BCC (Adopted from Mosterd et al 2011.)**

### 6.3.2 Pre-study Screening Visit biopsy specimens

Biopsy specimens will be processed by Saint Louis University Department of Dermatology’s Dermatopathology Laboratory for hematoxylin and eosin (H&E) assessment and immunohistochemical staining. Histologic assessment will be performed by a board-certified Dermatopathologist. If pathology of the target lesion does not demonstrate basal cell skin cancer, the subject will be excluded from the study.

Breslow depth or “invasion index” of deepest basal cell skin cancer cells will be recorded. This may include small nests of cells outside of the bulk of the tumor.

The thickness of the tumor will be measured from below the stratum corneum to the bottom of the deepest tumor nest using an ocular micrometer (Pierre Verniers method) to the precision of 0.1 mm. Tumor thickness and investigation of disease-free deep margin will be defined as at least 0.1 mm of tumor-free tissue.

If more than one sampling biopsy was performed on a target lesion, the most aggressive subtype and the depth of the deepest tumor cells on any biopsy will be recorded.

In tumors with multiple subtypes, a diagram will be created to denote areas of each histological subtype to determine anatomic location of cells of different subtypes and depth of tumor cells of different histological subtype.

Photography of pathologic slide will be performed.

Immunohistochemical evaluation of tumor tissue will also be performed in order to estimate the cellular density and composition of the pre-treatment lesion.

### 6.3.3 **Week 12 and Week 24 Visit biopsy specimens**

- Week 12 and Week 24 biopsy specimens will be processed and examined in the manner outlined for biopsies performed during the screening visits.
- **Residual tumor**
  - Evidence of any histologic change in residual tumor tissue compared to pre-treatment biopsy specimens
  - Estimate of changes in cellular density and composition compared to screening visit
- **Area of Tumor Clearance**
  - Assessment of histologic clearance in areas of apparent clinical tumor clearance

Additional immunohistochemical staining with anticytokeratin (AE1/AE3) and Ber-EP4 will be performed to delineate tumor from inflammation when necessary.

### 6.3.4 **Surgical Excision specimen**

Pathologic evaluation of “debulking” specimen and “tumor margins” specimen will be performed in the manner of the biopsy and Week 12 specimens. Breslow depth of area this measurement will be used to determine quantitative histological response of deepest part of lesion. Histopathologic subtype(s) will be recorded, and comment made as to tissue location of each subtype noted. Photography of surgical specimens will also be performed. In a manner as performed on biopsy specimen, diagram will be created to include tracing of different areas of histological subtype. Depth of deepest tumor cells will be recorded. A percentage estimate will be determined as to the histologic subtypes of the majority of tumor cells within the surgical specimen.

### FUTURE USE OF BLOOD, TISSUE OR DATA

The investigator will request permission from subjects to allow tissue to be used in the future for research purposes. Subjects may decline future use of tissue. The specimens taken during the tissue collection as specified for this research study include the sample to be used in the future. No extra tissue will be taken for future research purposes.

The tissue may be used to further evaluate Basal Cell Skin Cancer. All tissue specimens will be labeled with a study ID code, and study assigned pathology number. The investigator will maintain a list of the participants and code numbers in a locked file with access limited to the study team.

The investigator may share the tissue (with code only) with other researchers at Saint Louis University and at other research centers. Other investigators will not have access to identifying information.

All specimens will be kept indefinitely, and will be maintained in the Biospecimens Accessioning and Processing (BAP) Core Lab at Mayo Clinic Florida. .

## **6.4 INTERCURRENT DISEASE TREATMENT AND CONCOMITANT MEDICATIONS**

### **6.4.1 Intercurrent Disease Treatment**

Subjects who develop additional tumors during the study may receive conventional forms of treatment for the non-target tumors during the treatment and follow-up periods if the following criteria are met:

- The tumor(s) are sufficiently distal from the target tumor to prevent interference with the target tumor (at least 5 cm)
- The treatment is not listed in Exclusion Criteria
- The treatment will not affect the target lesion(s)

### **6.4.2 Concomitant Medications**

The investigator will record any medications given in treatment of AEs on the appropriate CRF page. Any medication taken by the subject during the course of the study should also be recorded on this form. Local anesthetics used for pre-study biopsies and target tumor excisions need not be recorded. Over-the-counter medicinal products (dietary supplements, herbal medications, etc) should also be recorded. Data recorded will include name of the medication, dose, unit, frequency, route, indication, and start and stop dates.

## **6.5 SUBJECT COMMITMENT TO STUDY**

The duration of each subject's participation in the study will be approximately 28 weeks. Subjects will be expected to visit the clinic for 10 scheduled study visits. Up to 12 (three sampling biopsies on 4 possible target lesions) will be performed at the pre-study screening visit, 12 punch biopsies at Week 12 visit and a complete Mohs excision may be performed at the target tumor site at the Mohs procedure visit within 4 weeks after the end-of-treatment visit. Subjects are expected to adhere to daily administration of medication during 24 weeks of treatment and take appropriate measures to avoid pregnancy and avoid donation of blood up to 9 months after last dose.

## **6.6 SUBJECT WITHDRAWAL OR DISCONTINUATION**

### **6.6.1 Subject Stopping Criteria**

The following objective measures have been defined as subject stopping criteria. If a subject presents with any of these characteristics, treatment with vismodegib will be stopped before 24 weeks:

- 1) Pregnancy
- 2) 20% increase in target lesion tumor size

#### 6.6.2 **Other Withdrawal or Discontinuations**

Subjects may withdraw themselves or have the investigator withdraw them from the study at any time without prejudice to their future medical care. Any subject who does not comply with the inclusion/exclusion criteria will be withdrawn from further participation in the study. Subjects may also be discontinued if the investigator has determined that the subject has AEs of severe intensity or duration to warrant discontinuation. If a subject discontinues due to AE, the subject will be followed until the AE has resolved.

Any subject who receives study medications or placebo must complete EOT procedures including the Mohs surgical excision, and the investigator must complete the end-of-study Subject Status form.

The investigator is encouraged to carefully select subjects who are likely to complete all study procedures.

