### 1.3 POTENTIAL RISKS AND BENEFITS

The safety, preliminary efficacy, and pharmacokinetics of vismodegib in mBCC and laBCC were assessed in an open-label, multicenter, two-stage Phase I trial. Patients with solid tumors refractory to standard therapy were treated until disease progression, intolerable toxicities, or withdrawal from the study. Thirty-three patients with mBCC or laBCC were included in analysis and followed over a 20-month period. Assessment using the RECIST criteria version 1.0 was completed if tumors had radiologically measurable disease. Otherwise, pre-defined clinical response measures were employed. An overall response rate of 58% was observed. (Von Hoff et al 2009) The most common response, in 17 of 33 cases, was partial response. Complete response was seen in 2 cases. Stable disease was observed in 12 cases. (Von Hoff et al 2009) No dose-limiting toxic events or grade 5 events were observed with a single grade 4 adverse event (asymptomatic hyponatremia) reported. The more significant and frequent adverse events were GI related with dysgeusia and muscle spasm reported.

Further evidence of the efficacy of vismodegib in the treatment of BCC was shown in the pivotal ERIVANCE trial, a Phase II single-arm, non-randomized trial of single-agent vismodegib at 150 mg/day to progression or intolerance with 104 patients enrolled: (33 mBCC, 71 LA BCC). The study met its primary endpoint overall response rate (ORR) by an independent review facility (IRF) and showed shrinkage of tumors in a pre-defined percentage of patients. A preliminary safety assessment showed the most common adverse events were consistent with previous experience with vismodegib. The most common adverse events were muscle spasms, hair loss, altered taste sensation, weight loss, fatigue, nausea, decreased appetite and diarrhea. A detailed safety assessment is ongoing.

Therapy with vismodegib has the potential to significantly decrease morbidity of the patients' BCC either through complete clearance of tumor or by substantially decreasing the morbidity of surgery. Though BCC expected to respond favorably to treatment with vismodegib, surgical excision by MMS will occur within 6 months of initial consultation; this study will not adversely affect the current standard of care in the management of BCC in non-responders.

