#### 6.1.1 Pre-study Screening visit

Subjects will be screened within 4 Weeks (+/-3 days) prior to the Treatment Initiation (Baseline/Day 1) visit to confirm that they meet the entrance criteria for the study. The study investigator or sub-investigator will discuss with each subject the nature of the study, its requirements, and its restrictions. Written informed consent must be obtained prior to performance of any protocol-specific procedures.

The following procedures will be performed at Pre-study Screening visit, within 4 weeks prior to Treatment Initiation (Baseline/Day 1, Visit 2) visit

- Confirmation of inclusion criteria, excluding histologic confirmation of basal cell skin cancer of target lesion.
- Identification of skin lesion(s) clinically suspicious for basal cell skin cancer.
- Recording of medical history. (Medical history is defined as a disease or syndrome that is ongoing at or stopped before Informed Consent.)

- Recording of history of alcohol and drug use, smoking status (current smoker, current heavy smoker >20 cigarettes per day), and average weekly alcohol consumption (units/week), where a unit contains 12 g of pure alcohol, an amount equivalent to that contained in 5 oz (a glass or 148 mL) of wine, 12 oz (355 mL) of beer, or 1.5 oz (44 mL) of 90 proof of spirits. (The intent is to monitor the subject's alcohol consumption during the study to determine if it has impact on the efficacy, disease state and any co-morbidities. It is the PI's discretion to determine acceptable levels of consumption or abuse. Alcohol and/or substance abuse are exclusionary.)
- Recording of current medications and all other drugs (including non-prescription drugs, vitamins, and dietary supplements) taken within 4 weeks prior to Screening.
- Complete physical examination including full-body skin exam.
  - Physical examination includes: height, weight, general appearance, skin (other than primary diagnosis), HEENT (head, eyes, ears, nose and throat), heart (auscultation), lungs (auscultation), abdomen (palpation and auscultation), lower extremities (peripheral edema), neurologic (mental status, station, gait, reflexes, motor and sensory function, coordination) and lymph nodes.
- Vital signs [blood pressure (BP); heart or pulse rate; and oral, tympanic, or temporal temperature].
- Males are reminded that they must use effective measures to avoid pregnancy in their partner at all times, even after vasectomy, for 3 months after the last dose.

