#### 6.1.5 Early Termination

If a subject discontinues from the study early (due to patient decision to discontinue or disease progression), the study procedures will be completed as described for Week 24.

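### Section 6.6.2 makes Mohs excision mandatory for dosed subjects, against the biopsy-dependent rule that Section 6.1.5 applies to early discontinuers; the 24-week schedules also omit the Week 24 biopsy

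*Combined protocol and SAP*

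**What the plan says.** Section 6.6.2, on withdrawal and discontinuation, contains the sentence "Any subject who receives study medications or placebo must complete EOT procedures including the Mohs surgical excision". The same section opens with the right to leave: "Subjects may withdraw themselves or have the investigator withdraw them from the study at any time without prejudice to their future medical care". Section 5 gives a similar assurance that withdrawing will not alter the patient's care.

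Section 6.1.5 sets the rule for early termination: "the study procedures will be completed as described for Week 24". It gives the reasons for stopping in brackets: "due to patient decision to discontinue or disease progression". Section 6.6.1 lists two mandatory reasons to stop treatment, pregnancy and a "20% increase in target lesion tumor size". Section 6.6.2 adds discontinuation for adverse events.

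The Week 24 procedures are in Section 6.1.4. All subjects are biopsied. Residual histologic disease leads to excision within 4 weeks of the last dose, and its absence leads to observation. Sections 3 and 6.1.6 make surgery depend on histology in the same way. Sections 6.1.2 and 6.1.3 send Week 12 complete responders with no histologic disease to observation. Section 6.5 tells subjects that "a complete Mohs excision may be performed at the target tumor site", which is permissive.

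Appendix 6 has two schedules that run to Week 24, one ending in surgery and one in observation. Both mark the punch biopsy at screening and Week 12 only.

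**The concern.** Two sections give different instructions on whether an operation is required. A site handling an early discontinuation would naturally open Section 6.6.2, and there the excision is unconditional. A subject who stops by choice or because of an adverse event, and whose biopsy shows no tumor, could be told that surgery is obligatory. That is hard to square with the right to withdraw stated in the same section and in Section 5. It also runs against the rationale in Section 1.1, which includes sparing surgery in selected lesions.

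The schedule gap adds to this. The Week 24 biopsy decides between surgery and observation, and a site working from the Appendix 6 tables alone would not take it.

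**Working it through.** No figure in the plan depends on the Section 6.6.2 sentence, so the check is mainly a comparison of text.

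**1. What each rule requires**

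| Subject | Section 6.6.2 as written | Visit-level rule | Result |
|---|---|---|---|
| Stops early by choice or for progression, biopsy positive | Mohs excision | 6.1.5, then 6.1.4: excision | Agree |
| Stops early by choice or for progression, biopsy negative | Mohs excision | 6.1.5, then 6.1.4: observation | Direct conflict |
| Stops for an adverse event or pregnancy | Mohs excision | 6.1.5 does not name these reasons | Biopsy rule not expressly applied |
| Week 12 complete clinical and histologic response | Mohs excision, if read literally | 6.1.2 and 6.1.3: observation | Literal conflict only |
| Week 24 completer, biopsy negative | Mohs excision, if read literally | 3 and 6.1.4: observation; 6.1.6 reserves surgery for positive biopsies | Literal conflict only |

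The direct conflict is in the second row. The third row is a gap in coverage. In the last two rows a site has a clear instruction from the section that governs the visit, and the heading and preceding paragraph of 6.6.2 suggest that its sentence is aimed mainly at discontinuers.

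**2. Week 24 biopsy in Appendix 6**

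- Surgery schedule: punch biopsy marked at screening and Week 12. The pathology rows are marked at screening, Week 12 and the surgery visit, not at Week 24.
- Week 24 complete-response schedule: punch biopsy marked at screening and Week 12. It has no pathology rows.
- Count: the Week 24 biopsy is marked in 0 of 2 schedules, although Section 6.1.4 requires it of all subjects and Section 6.3.3 describes how the specimens are examined.

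A table broken in conversion is an unlikely explanation, because the prose of Section 6.5 also lists biopsies at screening and Week 12 and none at Week 24.

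**3. The six-month statement in Section 1.3**

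Section 1.3 says that "surgical excision by MMS will occur within 6 months of initial consultation". The inputs are the screening window in Section 6.1.1 ("Subjects will be screened within 4 Weeks (+/-3 days) prior to the Treatment Initiation (Baseline/Day 1) visit"), 24 weeks of treatment (Section 3), and surgery within 4 weeks of the last dose (Section 6.1.6).

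- Longest planned interval: 4 + 24 + 4 = 32 weeks = 224 days; 224 / 30.44 = 7.4 months.
- With the 3-day allowance: 28 + 3 + 168 + 28 = 227 days; 227 / 7 = 32.4 weeks.
- Six months: 6 × 30.44 = 182.6 days; 182.6 / 7 = 26.1 weeks. After 24 weeks of treatment this leaves about 2.1 weeks for screening and surgical scheduling together.

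The permitted windows can therefore exceed the stated six months, if the initial consultation is taken to be the screening visit.

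**The case against.** The best defence is that Section 6.6.2 speaks of end-of-treatment procedures, that these are defined in Section 6.1.4, and that the biopsy condition comes with them. The rest of the protocol is consistent on this, and the placebo reference suggests leftover template text. The consistency elsewhere is real, and it is why the conflict for responders and completers is only literal. But the sentence says that dosed subjects must complete procedures including the excision. That wording does not carry a condition, and it is current text even if it was inherited.

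A second objection is that adverse-event discontinuers are not left to Section 6.6.2. Section 3 provides an early termination visit without limiting the reason, Section 9.3.2.2 speaks of adverse effects that lead to early termination, and Section 6.1.8 follows all subjects for a year after stopping drug. This stands. A reader might infer that Section 6.6.2 alone governs these subjects. The documents do not support that, and the Appendix 5 algorithms, which might address early stoppers, are not in the available text. What can be said is that the Section 6.1.5 brackets do not expressly name adverse events or pregnancy.

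A third objection is that the six-month wording is background text whose final clause concerns non-responders, and that the comparison rests on an assumed starting point. This also stands, so it is at most a minor correction.

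**Conclusion.** The point holds as an internal contradiction that should be corrected. For early discontinuers with a negative biopsy, Section 6.6.2 requires surgery and Sections 6.1.5 and 6.1.4 require observation. The missing Week 24 biopsy in both 24-week schedules is a separate, verifiable error in a table that sites follow. The number of subjects affected cannot be derived, because the documents give no expected rate of early discontinuation or of negative biopsies among those who stop.

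Stronger readings are tempting but not supported:

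- A reader might infer that every treated subject must have surgery and that the observation pathway is void. Sections 3, 6.1.2, 6.1.3, 6.1.4 and 6.1.6 direct responders and completers clearly.
- A reader might infer that the sentence undermines the primary efficacy analysis. The clinical response categories and the Week 12 and Week 24 biopsy assessments do not depend on it. The excision-specimen comparisons cover only subjects who have an excision because of how the trial is designed, and saying so in the analysis section would change no result.
- A reader might treat Section 1.3 as a broken commitment. The figure of about 32 weeks against 26.1 weeks depends on equating initial consultation with screening.

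**What to change.** 1. Replace the Section 6.6.2 sentence with: *A subject who received study drug and stops early will be asked to complete the Week 24 assessments, biopsy included (Sections 6.1.4 and 6.1.5). Excision is performed, with the subject's agreement, if histologic disease is found, as in Sections 6.1.4 and 6.1.6.* Delete the placebo reference and keep the Subject Status form requirement.
2. Reword the brackets in Section 6.1.5 to cover stopping for any reason, including adverse events and pregnancy, with biopsy and surgery in pregnancy left to clinical judgment.
3. In both 24-week schedules of Appendix 6, mark the Week 24 punch biopsy and its pathologic evaluation. The complete-response schedule needs a pathology row for this.
4. Optional: in Section 1.3, replace the six-month figure with the interval that the windows allow, about 32 weeks from screening, or 227 days with the 3-day allowance.

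The new wording should not add an excision rule for clinically visible tumor with negative histology. That would be a new treatment rule, contrary to Sections 6.1.4 and 6.1.6.

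The cost is a protocol amendment limited to wording and schedule entries. Sample size and visits do not change, and the Week 24 biopsy is already required by Section 6.1.4.

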#### 6.7 **TREATING OVERDOSE**

Overdose is unexpected due to the dose level administered with oral administration. There is no information on overdosage in humans. In clinical trials, vismodegib capsule was administered at 540 mg orally once daily; exposure did not increase between 150 mg and 540 mg daily.

#### 6.8 **PREGNANCY**

Vismodegib is teratogenic. As clinical studies of vismodegib have not been conducted in pregnant humans, subjects who become pregnant during the study must inform the investigator immediately of their pregnancy, and agree to provide follow-up information regarding the outcome of the pregnancy. In addition, there is the unknown potential irreversible affect on fertility with data showed in earlier studies of amenorrhea. Subjects (male and female) who desire to conceive in the future are excluded from the study.

Females of reproductive potential must use effective measures to avoid pregnancy during therapy and for 1 month prior to the start of the study medication, and for 9 months after completing therapy. Male patients must use effective measures to avoid pregnancy in their partner, even after vasectomy, during sexual intercourse with females during treatment and for 3 months after the last dose to avoid exposing a pregnant partner and the unborn fetus to vismodegib. Vismodegib is contraindicated in nursing mothers during treatment and for 9 months after the last dose. In addition, subjects will be instructed not to donate blood or blood products while on treatment and for 9 months after the last dose of vismodegib.

The anticipated pregnancy prevention program includes the following measures for women of childbearing potential:

- a) two negative pregnancy tests with a sensitivity of at least 25 mIU/mL at least 19 days apart prior to starting study medication. For patients with regular menstrual cycles, the second pregnancy test should be done during the first 5 days of the menstrual period immediately preceding the beginning of therapy and after the patient has used 2 forms of contraception for 1 month. For patients with amenorrhea, irregular cycles, or using a contraceptive method that precludes withdrawal bleeding, the second pregnancy test must be done immediately preceding the beginning of therapy and after the patient has used 2 forms of contraception for 1 month.
- b) Urine pregnancy test at each visit.
- c) Female patients must use 2 effective methods to avoid pregnancy for 1 month prior to start of study medication, during therapy, and for 9 months after completing therapy.

Male patients must use effective measures to avoid pregnancy in their partner at all times, even after vasectomy, for 3 months after the last dose (condom with spermicide is the effective method of contraception per approved labeling for vismodegib).

- a) Study medication will NOT be dispensed at each visit until the results of pregnancy have been reviewed by the study investigator.
- b) Reminder to use effective measures to avoid pregnancy will be performed throughout the study treatment for both men and women

Female patients do not have to follow the aforementioned measures to avoid pregnancy IF they agree to abide to the following conditions:

- have stopped having their period for 12 months in a row (menopause) and their doctor says they are in menopause or clinically fit the criteria for menopause
- had both of their ovaries or uterus taken out by surgery
- their ovaries do not work and they cannot get pregnant (confirmed by their doctor)

